1. STUDY PROTOCOL

Name of Company:	Shijiazhuang Junlebao Dairy Co.,Ltd.
Study Product:	Lactobacillus paracasei N1115 versus placebo
Study Centre:	Atlantia Food Clinical Trials Ltd
Study Title:	A randomised, double-blinded, parallel, placebo-controlled study to investigate the efficacy of Lb paracasei [Junlebao Lp. N1115] as a probiotic to enhance gut development in young children
Study Design	Randomised, parallel, double-blinded, controlled
Objectives:	
Primary Objectives
 
 - Intestinal health (stool frequency, stool consistency, GI symptoms including flatulence, bloating, cramps and diarrhea) 
Secondary Objectives
 
 - Gut microbiota composition - Incidence of UTI - Antibiotic usage
Population:	Children born by Caesarean Section, aged between 6 months and 3-years old
No. of volunteers:	Screen: n = 90 Randomize: n = 60 (30 per group)
Treatment:	Lactobacillus paracasei N1115 versus placebo
Duration/No. of visits:	4 Visits (Screening, Weeks 0, 4 &8)
Inclusion Criteria:	
To be eligible for inclusion, the subject must fulfill all of the following criteria:
 
 1. Male or female subjects aged \geq 6 months and \leq 3 years, 2. Parent/Guardian has given written informed consent, 3. Be in generally good health as determined by the investigator.
Exclusion Criteria:	
The presence of any of the following criteria will exclude the subject from participating in the study:
 
 1. Are currently taking probiotics or prebiotics, or have taken them in the past 2 weeks, 2. Unwilling to avoid probiotics / prebiotics for the duration of the study, 3. Have a significant acute or chronic coexisting illness (cardiovascular, gastrointestinal, endocrinological, immunological, metabolic or any condition which contraindicates, in the investigators judgement, entry to the study), 4. Having a condition or taking a medication that the investigator believes would interfere with the objectives of the study, pose a safety risk or confound the interpretation

	of the study results, 5. Subjects have taken antibiotics within the past 3 months (history of antibiotic use in previous 6 months recorded), 6. Subjects may not be receiving treatment involving experimental drugs, 7. If the subject has been in a recent experimental trial, these must have been completed not less than 60 days prior to this study.
Washout:	14 days from probiotics & prebiotics
Optional: daily eDiary:	Parent/Guardian would be provided with a tablet PC and be instructed to record daily bowel frequency, stool consistency and GI symptoms (including flatulence, bloating, cramps) of their child. Parent/Guardian would complete the diary daily for the 2 weeks prior to randomization and for the intervention period of 8-weeks.
Analysis	
 • Fecal microbiota • Fecal water metabolomics • Energy levels of infants-how to monitor it? • Level of antibiotic usage • Salivary cortisol

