2. STUDY PROCEDURES

Study preparation:

Design and compile case report form (CRF) and questionnaires. Site initiation visit and training of clinical staff on all aspects of the study will be performed.

Subjects will be randomly assigned to placebo or study product and all study personnel and participants will remain blinded for the duration of the study.

This study will be conducted in accordance with ICH GCP.

The visit windows are set as outlined in the table & text below, but if exceptional circumstances occur then this window can be extended at the discretion of the Principal Investigator. To date there have been no visit window deviations.

STUDY:				
Visit Number	Visit 1	Visit 2	Visit 3	Visit 4
Visit	Screening	Week 0	Week4	Week 8
Window	-28 to -14 days			
Informed Consent	x			
Inc/Excl.	x	x		
Demographic data	x			
Medical History	x			
Anthropometric Measurements (Weight,	x	x	x	x

height, BMI)				
Stool sample				
Saliva sample				
Randomization			x	
Admin Study Product		x	x	
Return Product/Compliance			x	x
Prior/con meds	x	x	x	x
AE/SAE		x	x	x
Optional:				
Daily eDiary (electronic device to capture daily reports/symptoms)	Stool Frequency, Consistency, GI Symptoms (including flatulence, bloating, cramps)			

Sample Collection & Processing:

Stool Samples: Subjects are instructed to collect a stool sample before attending Visit 2, Visit 3 and Visit 4. Each parent/guardian is provided with a stool collection kit with two stool sample containers, and instructed to collect a sample the night before the visit, and again on the morning of the visit. If the child produces a sample on the morning of the visit, the sample collected the previous evening is discarded. Once the sample is delivered to the Atlantia clinic, it is placed in a refrigerator and collected by Teagasc. This collection occurs each day samples are delivered onsite by subjects.

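### The only instrument described for the primary outcomes, the daily eDiary, is marked optional in both the synopsis and the visit schedule

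*Protocol*

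**What the plan says.** The Objectives row of the synopsis (Protocol, section 1) gives the primary objective as "Intestinal health (stool frequency, stool consistency, GI symptoms including flatulence, bloating, cramps and diarrhea").

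Further down the synopsis, the row describing how these are recorded is headed "Optional: daily eDiary". It is written in the conditional: "Parent/Guardian would be provided with a tablet PC", and "Parent/Guardian would complete the diary daily for the 2 weeks prior to randomization and for the intervention period of 8-weeks". The next row, Analysis, contains an item that is still an open question: "Energy levels of infants-how to monitor it".

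In the visit schedule (Protocol, section 2) the last block again carries an optional heading. Under it stands "Daily eDiary (electronic device to capture daily reports/symptoms"), with the content "Stool Frequency, Consistency, GI Symptoms (including flatulence, bloating, cramps"). No other row of the schedule names these outcomes.

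Section 2 also says that a CRF and questionnaires will be designed, and that the analysed data come from the CRFs. It does not say what either contains. Stool samples are to be brought to Visits 2, 3 and 4.

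**The concern.** Whether the primary outcome must be collected is settled in the protocol. An analysis plan can say how diary data are summarised, but it cannot make families record data that the protocol leaves optional. The monitor is asked to check conduct against the protocol, and on this text a missing diary would not be a deviation.

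The word *optional* has two natural readings, and the stakes differ.

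- **The sponsor has not decided whether to use the diary.** The conditional verbs and the unresolved item in the neighbouring row fit this reading. If the diary is not used, no described instrument collects the primary outcomes, before or after randomisation.
- **Each family may decline the diary.** No opt-out is stated, but the label allows it. The primary comparison then rests on the families who agree, with less precision and narrower applicability. If families stop after randomisation for reasons linked to symptoms, bias is also possible.

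A baseline not recorded before treatment starts cannot be collected later. In a randomised comparison that costs precision rather than validity.

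**Working it through.** The protocol states no figure on this point to reproduce. The check is a reading of every place where the primary outcomes could be collected, plus simple counts.

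**1. Schedule rows above the optional heading** (visit and window header rows excluded; row labels only, so shifted marks in the extracted table do not matter):

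1. consent
2. eligibility
3. demographics
4. medical history
5. anthropometry
6. stool sample
7. saliva sample
8. randomisation
9. product supply
10. product return and compliance
11. medications
12. adverse events

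Rows naming a primary outcome: 0 of 12. Rows naming a questionnaire: 0 of 12.

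**2. Analysis list in the synopsis:** faecal microbiota, faecal water metabolomics, energy levels, antibiotic use, salivary cortisol. Primary outcomes named: 0 of 5. The list may be meant for laboratory and additional measures, so this is supporting evidence only.

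**3. Other possible sources**

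| Source | What the protocol says | Can it supply the primary outcomes? |
|---|---|---|
| Stool samples | Collected for Visits 2, 3 and 4, refrigerated, passed on | No consistency scoring described; cannot give daily frequency or symptoms |
| Adverse event recording | A schedule row | May catch some events, such as diarrhoea; not described as an outcome measure |
| CRF and questionnaires | To be designed | Content, timing and schedule row not given; can be neither assumed nor excluded |
| eDiary | Frequency, consistency and symptoms, daily | Yes, but optional |

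**4. Contrast with the secondary objectives.** Microbiota has the stool samples and an Analysis item. Antibiotic use has the medications row and an Analysis item. Neither route is marked optional. The primary objective depends on an item that is.

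**5. Amount of data covered by the label** (sample size: "Screen: n = 90 Randomize: n = 60 (30 per group"))

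- Diary days per child: 2 × 7 + 8 × 7 = 14 + 56 = 70.
- Randomised children: 60 × 70 = 4,200 child-days, of which 60 × 14 = 840 are baseline and 60 × 56 = 3,360 are on intervention.
- Required stool samples: 60 × 3 = 180.

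These are planned quantities that the label leaves unsecured. They do not measure data already lost.

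**6. Fit of the baseline period.** Screening falls 28 to 14 days before Week 0, so at least 14 days are available for the two-week baseline. The visit structure already allows for the diary.

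**The case against.** The strongest reply is that *optional* may refer to the electronic device. Both descriptions tie the item to a tablet or electronic capture, and the same outcomes could be recorded on the planned CRF or questionnaires. On that reading nothing is lost and the fault is one of wording. The schedule is also visibly incomplete: questionnaires are planned without a row, and the secondary outcome of urinary tract infection has no row of its own, so the lack of a row does not prove lack of collection. Finally, the diary's respondent, content, frequency and duration are spelled out, which suggests that it was meant to be used.

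Part of this stands. The protocol does not show that any diary was withheld or any baseline missed, and the CRF may hold the data. The child-day counts describe planned work and do not measure harm. The severe consequence follows only if the sponsor may leave the diary out.

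It does not remove the point. No paper diary or alternative form is described, and the text nowhere says that the option concerns only the mode of capture. Under each reading the protocol names no required instrument for its primary outcomes. If a CRF page or questionnaire does the job, naming it and giving it a mandatory row closes the matter.

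**Conclusion.** The concern holds and must be fixed. The protocol attaches an explicit optional label, in two separate places, to the only described means of collecting its primary outcomes. It therefore requires no described collection of the primary data: 0 of 12 schedule rows above the optional heading cover them, while 70 planned diary days per child, including a 14-day baseline, sit under that label.

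Confidence in the text is high. The severity rests on the reading that the sponsor may choose not to deploy the diary; if only families may decline, the loss is mainly in precision and generalisability. The protocol gives neither an expected uptake nor a variance, so that loss is not quantified here. The conclusion is limited to what the protocol describes and requires, and makes no claim about what the CRF contains or what was done in practice.

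**What to change.** Remove *optional* from the synopsis row and from the schedule heading, replace the conditional verbs with firm ones, and make the daily eDiary a required procedure for the two weeks before randomisation and the eight weeks of intervention. Alternatively, name the CRF page or questionnaire that carries the primary outcomes and give it a mandatory row in the schedule. While editing, list diarrhoea in the diary content: the primary objective names it, while the diary descriptions cover it only through open-ended wording.

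The remark in section 2 that no visit window deviations have occurred so far suggests that the trial is under way. If so, apply the change by amendment to the remaining participants, and report diary completeness by arm, including the number of children with no baseline diary.

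The cost is small if the diary is already in use: two wording changes and an amendment. If it was not deployed, the sponsor must add tablets, training for staff and parents, and data handling. Because recording starts before randomisation, tablets may be needed for up to the 90 screened children (90 × 14 = 1,260 baseline days at most), fewer if devices are reused. Some unwilling families may be lost; the protocol gives no basis for a number. Each child enrolled without a diary before the change loses the baseline for good.

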2. STUDY PROCEDURES

Study preparation:

Design and compile case report form (CRF) and questionnaires. Site initiation visit and training of clinical staff on all aspects of the study will be performed.

Subjects will be randomly assigned to placebo or study product and all study personnel and participants will remain blinded for the duration of the study.

This study will be conducted in accordance with ICH GCP.

The visit windows are set as outlined in the table & text below, but if exceptional circumstances occur then this window can be extended at the discretion of the Principal Investigator. To date there have been no visit window deviations.

STUDY:				
Visit Number	Visit 1	Visit 2	Visit 3	Visit 4
Visit	Screening	Week 0	Week4	Week 8
Window	-28 to -14 days			
Informed Consent	x			
Inc/Excl.	x	x		
Demographic data	x			
Medical History	x			
Anthropometric Measurements (Weight,	x	x	x	x

height, BMI)				
Stool sample				
Saliva sample				
Randomization			x	
Admin Study Product		x	x	
Return Product/Compliance			x	x
Prior/con meds	x	x	x	x
AE/SAE		x	x	x
Optional:				
Daily eDiary (electronic device to capture daily reports/symptoms)	Stool Frequency, Consistency, GI Symptoms (including flatulence, bloating, cramps)			

Sample Collection & Processing:

Stool Samples: Subjects are instructed to collect a stool sample before attending Visit 2, Visit 3 and Visit 4. Each parent/guardian is provided with a stool collection kit with two stool sample containers, and instructed to collect a sample the night before the visit, and again on the morning of the visit. If the child produces a sample on the morning of the visit, the sample collected the previous evening is discarded. Once the sample is delivered to the Atlantia clinic, it is placed in a refrigerator and collected by Teagasc. This collection occurs each day samples are delivered onsite by subjects.

Saliva Samples: A saliva sample is collected from the subject during Visit 2, Visit 3 and Visit 4. The collection is carried out by a research nurse, who is trained according to Teagasc & Atlantia's standard operating procedure for the collection of saliva. The saliva sample is collected by inserting a swab into the child's mouth, letting it rest on the floor of the mouth for 30 seconds, allowing for soakage of any pooled saliva present. The swab is then rubbed on the child's tongue, roof of mouth and left and right buccal mucosa for 10 seconds each. Once collection has finished, the swab is placed into a vial and centrifuged at 1000g for 2 minutes. The separated saliva is aliquoted into a microtube and stored at -80°C. Once all subjects have completed the study and all samples have been collected, the samples will be shipped on dry ice for cortisol analysis.

QC, Data-entry& statistical analysis:

An independent study monitor will randomly review CRFs and source documentation to verify that the study is conducted in accordance with the protocol and GCP. After the last subject's last visit all data from the CRFs will be independently entered, verified and corrected and statistical analysis will be performed. A draft report will be presented to the sponsor and upon required revisions, the final version will be completed.

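### Could keeping either a morning or a previous-evening stool, with no stated home storage or collection time, bias the microbiota and metabolomics comparison?

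*Protocol*

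**What the plan says.** Under Stool Samples in section 2 of the protocol, a sample is required for Visits 2, 3 and 4. Each parent receives a kit with two containers and is "instructed to collect a sample the night before the visit, and again on the morning of the visit". The rule for choosing between them is "If the child produces a sample on the morning of the visit, the sample collected the previous evening is discarded". The protocol does not say outright what happens without a morning stool, but the reason for collecting in the evening is plainly to have a fallback.

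On storage it says "Once the sample is delivered to the Atlantia clinic, it is placed in a refrigerator and collected by Teagasc", and then "This collection occurs each day samples are delivered onsite by subjects". Time at the clinic is therefore short. For the time at home and in transit, the section gives no temperature, no maximum age, no recorded collection time and no note of which container was kept.

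The specimens serve a secondary objective in section 1, "Gut microbiota composition", and an item in its Analysis row, "Fecal water metabolomics". The primary objective (stool frequency, consistency and gastrointestinal symptoms) uses no specimen.

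The saliva paragraph gives no time of day for the cortisol sample, but says the nurse is trained to a "standard operating procedure for the collection of saliva", which is not shown.

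**The concern.** Which stool is analysed depends on whether the child passes one that morning. Stool frequency is part of the primary objective, so the trial itself entertains a product effect on it. Product is dispensed from Visit 2, so at Visits 3 and 4 specimen age could be a consequence of treatment. Randomisation and blinding do not remove a difference that arises after randomisation.

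If older stool also reads differently in the laboratory, part of an apparent product effect on microbiota or metabolites could be an effect of specimen age. The contrast with saliva, for which swab times, centrifuge settings and freezer temperature are all written down, makes the silence on stool before delivery stand out. The remark "To date there have been no visit window deviations" suggests that visits were under way, so a collection time not being recorded could not be recovered for those specimens.

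At stake are the interpretation of one secondary objective and one listed analysis.

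**Working it through.** The protocol gives no significance level, power, effect size or specimen age, so there is no figure of its own to reproduce. Only the sample size (60 randomised, 30 per group) and the collection rule come from the document. Every other input below is assumed.

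**Bias formula.** Let g be the difference between arms in the share of analysed stools that are morning stools. Let s be the assay shift, evening versus morning, in SD among specimens of the same age. Then bias = g × s. If either is zero there is no bias.

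**Type I error.** With 30 per arm, a t-test has 58 degrees of freedom. The noncentrality is bias / √variance × √15, where variance = 1 + p(1−p)s² and p is the morning share, near 0.5. Taking a two-sided 5% test:

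| g | s = 0.25 | s = 0.5 | s = 1.0 |
|---|---|---|---|
| 10 points | 0.025 SD, 5.1% | 0.05 SD, 5.4% | 0.10 SD, 6.3% |
| 20 points | 0.05 SD, 5.4% | 0.10 SD, 6.6% | 0.20 SD, 10.5% |
| 30 points | 0.075 SD, 5.9% | 0.15 SD, 8.6% | 0.30 SD, 17.8% |

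For scale, 30 per arm detects 0.736 SD with 80% power. A bias of 0.20 SD would be 0.20/0.736 = 27% of that, but it needs both a 20-point gap and a full-SD assay shift.

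**How large might g be?** Assume stools arrive at random at rate λ per day over 14 waking hours, with a 3-hour morning window and a 5-hour evening window.

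- Morning stool: m = 1 − exp(−3λ/14).
- Evening stool kept: e = (1 − m)(1 − exp(−5λ/14)).
- Morning share of analysed stools: m/(m + e).

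| λ per day | m | e | Morning share | g against λ = 1 |
|---|---|---|---|---|
| 1.0 | 0.193 | 0.242 | 44.3% | 0 |
| 1.5 | 0.275 | 0.301 | 47.8% | 3.4 points |
| 2.0 | 0.349 | 0.333 | 51.2% | 6.9 points |
| 3.0 | 0.474 | 0.346 | 57.8% | 13.5 points |

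The share moves slowly because a higher rate also raises the chance of an evening stool. A doubling stays below the 10-point row of the bias table, and a tripling does not reach the 20-point row.

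**Bias for a doubling.** At g = 0.069, bias is 0.069 × 0.25 = 0.017, 0.069 × 0.5 = 0.035 and 0.069 × 1.0 = 0.069 SD. Type I error is 5.05%, 5.2% and 5.6%. With assumed ages of 2 hours (morning) and 14 hours (evening), mean specimen age differs by 0.069 × 12 = 0.8 hours.

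**Chance imbalance.** At a morning share of 50%, the standard error of the arm difference is √(2 × 0.25/30) = 0.129, so the 95% range is ±1.96 × 0.129 = ±25 points. This exceeds the systematic shift, but it is sampling variation that the test already allows for.

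**Added noise.** With half the stools from the morning, variance is 1 + 0.25s² = 1.016, 1.062 and 1.25 for s = 0.25, 0.5 and 1.0. Thirty per arm is then worth 29.5, 28.2 and 24.0. Only the largest assumed assay shift costs much.

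**The case for a change.** The strongest case for acting is that the information is cheap to collect and cannot be recovered afterwards. Storage before delivery is a specimen procedure, not something an analysis plan can repair, and the protocol has a section for it. The stool model is uncalibrated. It varies only the rate, whereas a product that moved the time of day of defecation could open a wider gap. At one stool a day it also leaves 1 − 0.193 − 0.242 = 56.5% of children with no stool in either window, so it is only a rough guide. Small bias is thus made plausible and not proven.

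Those points about the model stand, as does the factual reading of the text. They do not show that the plan is wrong. Nobody would replace the morning-preferred rule: it favours the fresher stool and keeps a fallback where a strict morning rule would lose specimens. Silence in the protocol is not evidence that times go unrecorded or that stools sit warm. Parents are given a kit and instructions, and the case report form is listed as a preparation step; neither is reproduced.

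Nor would an arm difference be wholly invisible. The eDiary, although optional, records daily bowel frequency for 2 weeks before randomisation and through the 8 weeks of intervention. It lacks time of day, but it would show whether frequency had diverged by arm, which is one step in the chain.

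Not every stool at Visits 3 and 4 is exposed either: only a retained evening specimen is older. The missing time of day for saliva has no evident route to arm bias, and the procedure cited there may already fix it.

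**Conclusion.** No change to the plan is called for. The protocol allows specimens of two ages and does not write down home handling, but the rule it states is a fair trade-off between freshness and completeness. The unwritten part is detail that a site ordinarily puts in its kit instructions and case report form.

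The route to bias has two conditions, neither quantified in the document. Under the assumed stool model, a doubling of stool rate gives a 7-point gap in morning specimens, a bias of about 0.02 to 0.07 SD and a type I error of at most about 5.6%. The larger values, such as 10.5%, need a 20-point gap together with a 1.0 SD assay shift, and nothing in the protocol supports that pair. These figures rest on assumed collection windows, stool rates and assay shifts, with 30 per arm and a two-sided 5% t-test. They would understate the bias if the product moved the time of defecation strongly.

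The exposure is limited to one secondary objective and one listed analysis; the primary outcomes are untouched. Someone with access to the kit instructions and case report form could check that they cover home storage, collection time and which stool was kept, but that is site housekeeping and does not correct the design.
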